4 STUDY DESIGN

This is a prospective, non-randomized, single-arm study conducted under a common protocol designed to evaluate long-term outcomes following open treatment and implantation of the Rotation Medical Bioinductive Implant to treat insertional Achilles tendinopathy.

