4.1 SAMPLE SIZE

Up to 10 subjects will be enrolled and treated with the Rotation Medical Bioinductive Impant at Union Memorial hospital and the associated Surgery Center.

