4.3 PRIMARY OUTCOME MEASURES

4.3.1 Increase in Tendon Thickness

Achilles tendon thickness will be measured pre-operatively (baseline) and the total thickness of the tendon and any newly induced tissue at the implant site will be measured at each follow-up visit using magnetic resonance imaging (MRI). The mean (\pm SD) change in post-operative Achilles tendon thickness will be calculated at each follow-up interval.

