4.3.2 Integration and Maturation of New Tissue

Integration and maturation of the newly induced tissue will be assessed by MRI at each post-operative follow-up. This outcome will assess, at a minimum, the following characteristics of the newly induced tissue: (i) presence or absence of a clear boundary between the device and the underlying tendon; (ii) maturation of newly induced tissue to resemble characteristics of underlying tendon tissue (versus debris, artifact, or calcification).

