4.4.2 Procedure Parameters

The following procedural parameters will be recorded on all subjects:

- 1. Device implant time: Mean (\pm SD) implant time defined as follows:
 - Open procedure: Time from introduction of the bioinductive implant into the surgical field to completion of the last staple
- 2. Procedure technical success: The proportion of subjects where the device was successfully delivered and affixed to target tendon location.
- 3. Device implant position: An intra-operative photograph(s) or video recording showing the implant location of the device and all tendon and bone staples will be obtained.

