5 STATISTICAL ANALYSIS PLAN

This is an initial feasibility study and not powered to address the hypotheses. Changes in tendon thickness over the time of the follow up visits will be assessed by a Repeated Measures ONEWAY ANOVA with a post hoc Scheffe. Indices of new tissue integration and maturation at each follow up visit will be assessed by Chi Square analyses.

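### Chi-square is assigned to a primary outcome in one arm of at most 10 subjects without saying what is compared; neither plausible reading is sound, and no proportion is promised

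*Combined protocol and SAP*

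**What the plan says.** Section 4: "This is a prospective, non-randomized, single-arm study". Section 4.1: "Up to 10 subjects will be enrolled and treated with the Rotation Medical Bioinductive Impant".

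Section 4.3.2 lists integration and maturation among the primary outcome measures, read by MRI at the post-operative visits. Section 7.7 sets these at 3 months, 1 year and 2 years. The characteristics to be assessed include "presence or absence of a clear boundary between the device and the underlying tendon" and "maturation of newly induced tissue to resemble characteristics of underlying tendon tissue". The section names no summary statistic.

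Other outcomes do have one. For thickness, Section 4.3.1 says that the mean and SD of the "change in post-operative Achilles tendon thickness will be calculated at each follow-up interval". For technical success, Section 4.4.2 reports "The proportion of subjects where the device was successfully delivered and affixed to target tendon location".

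Section 5 gives the only analysis of integration and maturation: "Indices of new tissue integration and maturation at each follow up visit will be assessed by Chi Square analyses". It also states: "This is an initial feasibility study and not powered to address the hypotheses". No hypothesis is written out anywhere.

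**The concern.** A chi-square test needs something to compare: two or more groups, or observed counts against a stated null distribution. Here there is one arm. The indices have no baseline value, because the induced tissue exists only after surgery. No subgroup comparison is planned, no reference proportion is given, and no contrast between visits is named for these indices.

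The result at stake is the one a feasibility study of tissue induction most needs: how many of the subjects show integrated tissue, and how many show mature tissue, at each visit. If the sentence is followed as written, the analyst must invent a null or a contrast after the data are seen, and may report a p-value with no estimate beside it.

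**Working it through.** **Inputs from the documents.** One arm (Section 4); n at most 10 (Section 4.1); three post-operative visits in the same subjects (Section 7.7); integration scored as boundary present or absent (Section 4.3.2); chi-square, variant not named (Section 5).

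**Assumptions, because the documents give none.** Two-sided 5% level and 95% intervals; null proportions of 50 to 80%; maturation treated as yes/no; event rates of 60% or 70% and the within-subject correlations shown below. There is no figure in the plan to reproduce, since the 10 subjects come without a power or precision calculation.

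**Step 1: what is compared?** The sentence on thickness speaks of change over the follow-up period. The next sentence, on integration and maturation, speaks of each visit. Literally, the second is a per-visit analysis. Read in parallel with the first, it could mean a comparison across visits. Both readings are checked.

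**Step 2: per visit.** With one group, the statistic for x successes in n against a null p0 is X² = (x − n·p0)² / [n·p0·(1 − p0)], on 1 degree of freedom. For x = 9, n = 10:

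| Assumed p0 | X² | p | Smaller expected count |
|---|---|---|---|
| 50% | 16/2.5 = 6.40 | 0.011 | 5 |
| 60% | 9/2.4 = 3.75 | 0.053 | 4 |
| 70% | 4/2.1 = 1.90 | 0.17 | 3 |
| 80% | 1/1.6 = 0.625 | 0.43 | 2 |

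The same data fall on either side of 0.05 according to a number that the plan does not state. The smaller expected count is n·min(p0, 1 − p0), so it cannot exceed 10 × 0.5 = 5 whatever the null.

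**Step 3: across the three visits.** A visit-by-outcome table holds up to 10 × 3 = 30 readings from at most 10 people, and Pearson's test treats them as independent. If a subject's yes/no readings have correlation ρ, differences between visits vary less than Pearson's formula assumes, by a factor of about (1 − ρ). The statistic then behaves roughly as (1 − ρ) times a chi-square on 2 degrees of freedom. For ρ > 0 it exceeds 5.99 less often than 5% of the time. Simulated size at n = 10 with no true change:

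| Setting | Correlation 0 | 0.3 | 0.5 | 0.7 |
|---|---|---|---|---|
| 60% rate, correlation on an underlying normal scale | about 4.3% | 2.2% | 1.2% | 0.5% |
| 70% rate, correlation between the yes/no readings | 4.7% | 1.7% | 0.6% | 0.1% |

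Both settings show a test that becomes too cautious as readings within a subject agree more.

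**Step 4: what an estimate would give.** The exact (Clopper-Pearson) 95% interval for x of n runs from the 2.5% quantile of Beta(x, n − x + 1) to the 97.5% quantile of Beta(x + 1, n − x); the upper limit is 1 when x = n. It needs no null. At n = 10:
- 7/10: 34.8 to 93.3%
- 9/10: 55.5 to 99.7%
- 10/10: 69.2 to 100% (lower limit 0.025^(1/10) = 0.692)

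**The case against.** The strongest reply is that the sentence was meant to parallel the one on thickness and so compares visits. A contrast then exists and no null is missing. That reading is plausible, and a reader who infers that the plan can contain no contrast at all goes further than the text allows. It does not rescue the analysis, because Pearson's test would still ignore the pairing.

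A reader might next infer that repeated readings counted as independent must produce false positives. Step 3 shows the opposite for positive correlation: the cost is lost sensitivity.

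A reader might also infer that chi-square fails at n = 10 because its approximation breaks down. The evidence is mixed. In the one-sample test, size exceeds the nominal 5% at assumed nulls of 70% and 90% (7.6% and 7.0%). At 50, 60 and 80% it equals that of the exact binomial test, so the shortfall from 5% there reflects discrete data. The missing null is the firmer ground. Nor does the plan mention a cross-table of integration against maturation, so no criticism is built on one.

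It is fair to say that stakes are low and that counts could be recovered from any table that is published. But lack of power does not supply a missing null or contrast, and the plan does not commit to publishing the counts. It is also fair that another small-sample interval would serve as well as Clopper-Pearson, and that scoring rules may sit in the MRI guideline, which is not among the documents.

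**Conclusion.** The point holds as a defect in the choice and specification of the analysis for a primary outcome, and it should be fixed. The plan does not identify the comparison. Per visit, the p-value is undefined until someone supplies a null, and for 9/10 it ranges from 0.011 to 0.43 over assumed nulls of 50 to 80%. Across visits, the test is valid only in the sense of being conservative, with a simulated size of about 2.2, 1.2 and 0.5% at assumed correlations of 0.3, 0.5 and 0.7 and a 60% rate. On both readings no proportion is promised.

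The nulls, rates and correlations are illustrations and not taken from the documents; the absence of a null, a named contrast and an estimate is a matter of the text. The documents rest no decision on these p-values, so the consequence is an uninformative report of a primary outcome and not a wrong decision.

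**What to change.** Replace the chi-square sentence in Section 5 with:

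> At each visit, the number and proportion of subjects read by MRI who show integration, and who show maturation, will be reported with exact 95% confidence intervals (number in each grade if an index is graded).

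The intervals do not address change over time. If that is also intended, say so and name one exploratory paired analysis per index in place of Pearson's chi-square: Cochran's Q over the three visits, exact McNemar for a named pair of visits, or Friedman if the index is graded. State in Section 4.3.2, or by reference to the MRI guideline, when maturation counts as present, since a proportion needs that rule.

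The cost is wording; scans and visits are unchanged. The intervals are wide: for 7/10 the width is 93.3 − 34.8 = 58.5 percentage points. Cochran's Q and Friedman drop any subject who misses a visit. Exact McNemar at the 5% level needs at least six subjects who change, all in the same direction (2 × 0.5⁶ = 0.031; five give 2 × 0.5⁵ = 0.0625). A paired test here can therefore only be exploratory, and the counts with intervals should be the main result.

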6 ELIGIBILITY CRITERIA

Subjects who meet all inclusion criteria (Section 6.1) and none of the exclusion criteria (Section 6.2) will be eligible to participate in the study.

Enrollment in the study occurs upon intra-operative confirmation that the subject meets all of the inclusion criteria and none of the exclusion criteria. Subjects who meet eligibility criteria and are enrolled will be followed per protocol through the end of the study (i.e., intent-to-treat). Subjects who do not meet the study eligibility criteria at the time of surgery will not be enrolled.

6.1 INCLUSION CRITERIA

Subjects enrolled in the study **MUST meet** all of the following criteria:

- 1. At least 21 years of age
- 2. Insertional Achilles tendinopathy requiring surgery
- 3. Chronic insertional Achilles tendinopathy lasting longer than 3 months unresponsive to conservative therapy including, but not limited to, pain medication, physical therapy and shoe modification
- 4. MRI of the Achilles within 60 days prior to the study procedure
- 5. Willing to comply with the prescribed post-operative rehabilitation program
- 6. Willing to be available for each protocol-required follow-up examination
- 7. Able to understand the informed consent process, including regulatory requirements such as HIPAA authorization, and document informed consent prior to completion of any study-related procedures
- 8. Ability to read, understand, and complete subject-reported outcomes in English

6.2 EXCLUSION CRITERIA

Subjects enrolled in the study **MUST NOT meet** any of the following criteria:

- 1. Achilles tendon tear
- 2. Previous Achilles tendon surgery on the index ankle
- 3. Genetic collagen disease
- 4. History of auto-immune or immunodeficiency disorders
- 5. History of chronic inflammatory disorders
- 6. Oral steroid use in last 2 months or injectable steroid use in last 4 weeks
- 7. History of heavy smoking (> 1 pack per day) within last 6 months
- 8. Hypersensitivity to bovine-derived materials
- 9. Hypersensitivity to Polylactic Acid (PLA) and Polyetheretherketone (PEEK) materials
- 10. Metal implants, fillings, shrapnel, and/or screws
- 11. Females of child-bearing potential who are pregnant or plan to become pregnant during the course of the study
- 12. Currently involved in any injury litigation or worker's compensation claims relating to the index ankle
- 13. Enrolled, or plans to enroll, in another clinical trial during this study that would affect the outcomes of this study
- 14. History of non-compliance with medical treatment, physical therapy/rehabilitation, or clinical study participation
- 15. History of cognitive or mental health status that interferes with study participation

7 STUDY ASSESSEMENTS

The schedule of protocol-required study assessments is provided in **Table 7.1**. Adverse event (AE) reporting as required and defined in **Section 8** begins at the time of enrollment (i.e. intra-operative confirmation of eligibility) and concludes at the end of the study.

Table 7-1: Schedule of Study Assessments

	Baseline	Procedure	3-Month	1 Year	2 Year
Study Evaluation	Within 60 Days of Surgery	Within 60 Days of Baseline	± 15 days	± 45 days	± 90 days
Informed Consent	✓				
Medical History & Exam	✓				
Eligibility Assessment	✓	√ ¹			
Enrollment (Date of Surgery)		✓			
MRI	√ ²		✓2	✓2	√ ²
Procedure Data		✓			
Medications	✓3	✓3	✓3	✓3	✓3
Adverse Events		✓4	✓4	✓4	✓4
Recovery/Satisfaction			✓	✓	✓
Questionnaire					
Revision/Additional Achilles Surgery			√ 5	√ 5	√ 5

¹Eligibilty confirmation will be performed at the time of the study surgery to ensure the patient meets eligibility criteria. Patients who do not meet study eligibility criteria will not be enrolled in the study.

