7.2 ENROLLMENT

Enrollment in the study occurs upon clinical confirmation that the subject meets all of the inclusion criteria and none of the exclusion criteria. Patients who do not meet study eligibility criteria at the time of the study procedure will undergo tendon repair at the discretion of the surgeon (without use of the Rotation Medical Bioinductive Implant) and will not be enrolled in the study. The date of the study surgery is defined as the enrollment date and all subjects who are enrolled in the study will be followed per protocol unless voluntary consent is withdrawn. All subjects enrolled into the study will be identified through a unique identifier.

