8 ADVERSE EVENT DEFINITIONS AND REPORTING

Adverse events are to be reported from the time of enrollment through the last study follow-up visit.

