8.1 DEFINITION OF ADVERSE EVENT (AE)

An Adverse Event (AE) is any undesirable clinical occurrence experienced by the subject. Any underlying disease that was present at the time of enrollment and prior to surgery that persists after surgery is not considered an AE.

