12 RISKS AND BENEFITS

12.1 RISKS AND RISK MITIGATION

Study patients will be informed of all known potential side effects and complications associated with the study assessments and study procedure prior to enrollment in the study.

There are no known incremental risks to the subject for participating in the study. The risks associated with participating in this study are the same as if the patient is treated outside of the study using the same commercially-available device and include the following potential risks of Achilles Tendinopathy surgery performed under general or regional anesthesia:

- Tissue inflammation
- The need for repeated surgery because tendons do not heal properly or tears
- Pain or stiffness that won't go away
- Fever and/or infection
- Complication from anesthesia
- Nerve or blood vessel damage
- Adverse reaction to device

In addition, subjects will be required to undergo MR imaging. MRI is generally a well-tolerated procedure and there is no ionizing radiation involved with MR imaging. The potential risks are minimal and include claustrophobia, coil element heating and peripheral nerve stimulation, although the latter two are considered highly unlikely, given that the subjects will be imaged within preset safety guidelines to eliminate peripheral nerve stimulation. Coil element heating ranges from a mild sensation of heat to a potential burn. This is considered highly unlikely, as the coils have all undergone extensive testing and clinical use, and special pads are placed surrounding all contact points.

All Investigators will undergo training and subjects will be screened and evaluated for medical histories/conditions that may compromise safe, successful completion of any of the study assessments or performance of the device. Subjects with a known hypersensitivity to bovine-derived materials will not be enrolled in the study.

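### The adverse-event start point and the exclusion for persisting disease can under-count procedure-related harm, and both conflict with other sections of the protocol

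*Combined protocol and SAP*

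**What the plan says.** Start of reporting:

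- Section 6: "Enrollment in the study occurs upon intra-operative confirmation that the subject meets all of the inclusion criteria".
- Section 7: AE reporting "begins at the time of enrollment (i.e. intra-operative confirmation of eligibility").
- Section 8: "Adverse events are to be reported from the time of enrollment through the last study follow-up visit".
- Section 7.2 uses other words: "Enrollment in the study occurs upon clinical confirmation", and then "The date of the study surgery is defined as the enrollment date". It adds that patients found ineligible at the procedure have a repair without the implant and are not enrolled.

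Definition: Section 8.1 opens broadly, counting any undesirable clinical occurrence. It then says that underlying disease present before surgery "that persists after surgery is not considered an AE". Worsening is not mentioned.

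What is meant to be captured: Section 4.4.1 counts deaths, all serious events, device- or procedure-related non-serious events and unanticipated device effects. Section 8.3 points to the known risks in Section 12.1 as the anticipated adverse events. That list of seven surgical risks includes "Complication from anesthesia" and "Pain or stiffness that won't go away".

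**The concern.** The protocol names a set of harms it expects and then applies two rules under which some of them need not be recorded. The first is a matter of timing: anesthesia precedes any intra-operative step, so its earliest complications can occur before the window opens. The second is a matter of definition: the subjects have chronic insertional Achilles disease (in the synopsis, pain for more than 3 months), so pain after surgery can be read as the old disease persisting.

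Each rule can only remove events from the count. In a single-arm study of up to 10 subjects, with no control group and no power claim, a complete description of harm is one of the main things the study can deliver. Events not recorded at the time are hard to recover later. The wording also lets two investigators code the same course differently.

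**Working it through.** The plan states no event rate, so there is no figure to reproduce. The check is a comparison of sections, followed by arithmetic for scale.

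**1. When the window opens.** Sections 6, 7 and 8 together place the start at a moment within the operation. Section 12.1 says that surgery is under general or regional anesthesia, so anesthesia has started by then. Section 7.5 puts the assessment of tendon integrity after incision, detachment and debridement, and Section 6.2 excludes a tendon tear. Confirmation may therefore come after incision; the documents do not fix the moment. Section 7.2 is not tied to an intra-operative step and would allow the whole day of surgery. The two descriptions cannot both define the start.

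**2. Who is covered.** Consent is obtained at baseline (Section 7.3). A consented patient found ineligible in the operating room has had anesthesia, and possibly an incision, but is not enrolled (Section 7.2). Such a patient's events are outside the AE rules.

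**3. The seven risks in Section 12.1 against the rules.**

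| Risk | Exposure |
|---|---|
| Anesthesia complication | Partly: missed if before confirmation, captured if later |
| Nerve or vessel damage | Partly: missed if it occurs at tourniquet, incision or exposure before confirmation |
| Lasting pain or stiffness | Partly: can be read as persisting disease; new pain or stiffness is still an AE; worsening is undecided |
| Other four (inflammation, repeat surgery, fever or infection, device reaction) | No specific gap found |

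Two of seven are exposed through the items quoted above, and three if early nerve or vessel damage is added. None is excluded in full.

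**4. Definition against anticipated events.** Sections 8.3 and 12.1 together make lasting pain or stiffness an anticipated adverse event. Section 8.1 excludes persisting underlying disease. Nothing says whether disease there includes its symptoms, or what happens if they worsen.

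**5. Scale.** Assume that the rate is subjects with the event divided by enrolled subjects, with n = 10 (the maximum in Section 4.1).

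- One missed event in an enrolled subject: 1/10 = 10 percentage points.
- Exact 95% interval for 0/10: upper limit 1 − 0.025^(1/10) = 30.8%.
- Exact 95% interval for 1/10: lower limit 1 − 0.975^(1/10) = 0.3%; upper limit, the 0.975 quantile of Beta(2, 9), = 44.5%.
- One event in a non-enrolled patient, if added to both numerator and denominator: 1/11 = 9.1 points.

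As illustration only, let p be an assumed per-subject event rate and f the assumed share of events before the window opens. The chance of recording at least one event in 10 subjects is 1 − (1 − p(1 − f))^10:

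| p | f = 0 | f = 1/4 | f = 1/2 |
|---|---|---|---|
| 2% | 18.3% | 14.0% | 9.6% |
| 5% | 40.1% | 31.8% | 22.4% |
| 10% | 65.1% | 54.1% | 40.1% |

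Neither p nor f comes from the documents.

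**The case against.** The best defense is that the protocol has several nets.

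- **Same-day recording.** Table 7-1 ticks adverse events in the procedure column, Section 7.4 records intra-operative complications on the Procedure CRF, and Section 7.2 dates enrollment to the day of surgery. A site could well record an early same-day event in an enrolled subject. This softens the gap but does not close it: Section 7.4 refers back to Section 8, whose window starts at enrollment, and Section 7.2 conflicts with the explicit gloss in Section 7. It does nothing for patients who are not enrolled.
- **The exclusion names disease, not symptoms.** Section 8.3 also indicates that the protocol regards lasting pain as an adverse event. This is a fair reading, but the text does not settle it, and worsening remains unaddressed.
- **Pain is recorded elsewhere.** VISA-A is given at baseline (Section 7.3), listed for 6 and 12 months (Table 7-2) and given at 1 year (Section 7.7.2). Clinical assessments, prescription medications, unscheduled visits and further Achilles surgery are also documented, and return to full activity is an outcome in Section 4.4.3. A reader might infer that persistent pain goes uncaptured; that is not so. What stands is that VISA-A is not a listed outcome in Sections 4.3 or 4.4 and has no analysis in Section 5, so it does not replace AE classification.
- **Low stakes.** Safety is a descriptive secondary outcome in an unpowered feasibility study. That limits the severity but does not remove the inconsistency.

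A reader might also infer that a subject with a serious early complication would for that reason never be confirmed as eligible. The documents do not support this: such a complication is not among the criteria in Sections 6.1 and 6.2.

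**Conclusion.** The point holds in a limited form. Read literally, the AE window opens after anesthesia has begun, the sections disagree on when enrollment occurs, consented patients found ineligible at surgery are not covered, and the Section 8.1 exclusion sits in tension with Sections 8.3 and 12.1. These rules can lower the count of procedure-related events and cannot raise it.

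Three stronger readings are not supported. The plan does not leave out two of the seven listed risks: at least two are partly exposed and none is wholly excluded. It cannot be said that the safety outcome does under-count, because no event rates are given and sites may record more than the literal rule requires. Nor is 10 points a minimum for every missed event: that figure applies to an event in one of 10 enrolled subjects (it is larger with fewer enrolled), while a non-enrolled patient added to 10 gives 9.1 points.

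The conclusion assumes a subject-level rate, which Section 4.4.1 does not define, and a literal reading of Sections 6, 7 and 8. The primary MRI outcomes are unaffected. The correction should be made because it is inexpensive and unrecorded events may not be recoverable.

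**What to change.** - **Start point.** Reconcile Sections 6, 7, 7.2 and 8 on one AE start, no later than the start of anesthesia for the study procedure, for every consented subject. Starting at consent would also cover events at the baseline MRI. Keep the enrollment definition separate from the AE start.
- **Non-enrolled patients.** List events in consented patients who are operated on but not enrolled separately, outside the rate denominator.
- **Section 8.1.** Limit the exclusion to pre-existing conditions that have not worsened from baseline. State that new or worsened pain or stiffness is recorded as an AE, as is persistent pain or stiffness judged related to the procedure or device, in line with Sections 8.3 and 12.1.

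The cost is aligned wording in about five places, a few more CRF entries, one additional listing, and AE counts that may be slightly higher. The change concerns data collection only and leaves clinical care as it is.
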